8.4. Safety Assessments

Planned time points for all safety assessments are provided in the SoA ([Section 1.3](#)).

8.4.1. Physical Examinations

- A complete physical examination will include, at a minimum, assessments of the Cardiovascular, Respiratory, Gastrointestinal and Neurological systems and skin.
- Investigators should pay special attention to clinical signs related to previous serious illnesses.
- Physical examinations will be performed and height and weight will be collected as indicated in [Section 1.3](#). The complete physical examination will be overseen by either the Investigator or a Sub-Investigator who is a physician. New abnormal physical examination findings must be documented and will be followed by a physician or other qualified staff at the next scheduled visit.

8.4.2. Vital Signs

- Temperature, pulse rate, O₂ saturation, respiratory rate, and blood pressure will be assessed.
- Blood pressure and pulse measurements will be assessed with a completely automated device. Manual techniques will be used only if an automated device is not available.

- Vital signs will be measured in a semi-supine position after 5 minutes rest and will include temperature, systolic and diastolic blood pressure, and pulse and respiratory rate.

8.4.3. *Electrocardiograms*

- Single 12-lead electrocardiograms (ECG) will be obtained as outlined in the SoA (see [Section 1.3](#)) using an ECG machine that automatically calculates the heart rate and measures PR, QRS, QT, and QTc (corrected using Fredericia's and Bazett's methods) intervals.
- The ECG will be performed within 1 hour after study treatment administration on visits with administration of study therapy.

8.4.4. *Clinical Safety Laboratory Assessments*

- See Appendix 2 ([Section 10.2](#)) for the list of clinical laboratory tests to be performed and to the SoA ([Section 1.3](#)) for the timing and frequency.
- Samples will be sent to the appropriate central laboratory(ies) following the procedure(s) described in the lab manual.
- The Investigator must review the laboratory report, document this review, and record any clinically significant changes occurring during the study as an AE. The laboratory reports must be filed with the source documents.
- Abnormal laboratory findings associated with the underlying disease are not considered clinically significant unless judged by the Investigator to be more severe than expected for the participant's condition.
- All laboratory tests with values considered clinically significantly abnormal during participation in the study or within 28 days after the last dose of study intervention should be repeated until the values return to normal or baseline or are no longer considered clinically significant by the Investigator or Medical Monitor.
 - If clinically significant values do not return to normal/baseline within a period of time judged reasonable by the Investigator, the etiology should be identified, and the Sponsor notified.
 - All protocol-required laboratory tests, as defined in Appendix 2 ([Section 10.2](#)), must be conducted in accordance with the laboratory manual and the SoA ([Section 1.3](#)).
 - If laboratory values from non-protocol specified laboratory tests performed at the institution's local laboratory require a change in participant management or are considered clinically significant by the Investigator (eg, SAE or AE or dose modification), then the results must be recorded.
- Assessment of blood cell counts and renal function will be monitored for anti-viral toxicity

8.4.5. Pregnancy Testing

- A serum pregnancy test will be performed at screening for all female patients of childbearing potential. Prior to treatment assignment, a urine pregnancy test will be performed. If the urine pregnancy test result is negative, the patient will be eligible for treatment assignment and the remainder of the Day 1 testing/procedures will be performed. If the urine pregnancy result is positive, the patient must not be assigned to treatment and should reflex to a β -HCG blood test before screen failing. See [Section 1.3](#).
- A urine pregnancy test will be performed prior to each treatment for female patients who are of childbearing potential. See [Section 1.3](#).

8.4.6. Suicidal Ideation and Behavior Risk Monitoring

This section is not applicable.

8.5. Adverse Events (AEs), Serious Adverse Events (SAEs), and Other Safety Reporting

- The definitions of AEs and SAEs can be found in Appendix 3 ([Section 10.3](#)).
- The definitions of unsolicited and solicited AEs can be found in Appendix 3 ([Section 10.3](#)).
- AEs will be reported by the participant (or, when appropriate, by a caregiver, surrogate, or the participant's legally authorized representative).
- The Investigator and any qualified designees are responsible for detecting, documenting, and recording events that meet the definition of an AE or SAE and remain responsible for following up all AEs OR AEs that are serious, considered related to the study intervention or study procedures, or that caused the participant to discontinue the study intervention or study (see [Section 7](#)).
- The method of recording, evaluating, and assessing causality of AEs and SAEs and the procedures for completing and transmitting SAE reports are provided in Appendix 4 ([Section 10.6](#)).

8.5.1. Time Period and Frequency for Collecting AE and SAE Information

- All AEs and SAEs will be collected at the time points specified in the SoA ([Section 1.3](#)) from signing of informed consent until study participation is complete.
- Medical occurrences that begin before treatment assignment but after obtaining informed consent/assent will be recorded as Medical History/Current Medical Conditions, not as AEs.
- All SAEs will be recorded and reported to the Sponsor or designee immediately and under no circumstance should this exceed 24 hours, as indicated in Appendix 3 ([Section 10.3](#)). The Investigator will submit any updated SAE data to the Sponsor within 24 hours of it being available.
- Investigators are not obligated to actively seek information on AEs or SAEs after conclusion of the study participation. However, if the Investigator learns of any SAE,

including a death, at any time after a participant has been discharged from the study, and he/she considers the event to be reasonably related to the study intervention or study participation, the Investigator must promptly notify the Sponsor.

8.5.2. Method of Detecting AEs and SAEs

Care will be taken not to introduce bias when detecting AEs and/or SAEs. Open-ended and non-leading verbal questioning of the participant is the preferred method to inquire about AE occurrences.

8.5.3. Follow-up of AEs and SAEs

After the initial AE/SAE report, the Investigator is required to proactively follow each participant at subsequent visits/contacts. All SAEs, and AEs of special interest (as defined in [Section 8.5.7](#)), will be followed until resolution, stabilization, the event is otherwise explained, or the participant is lost to follow-up (as defined in [Section 7.4](#)). Further information on follow-up procedures is provided in Appendix 4 ([Section 10.6](#)).

8.5.4. Regulatory Reporting Requirements for SAEs

- Prompt notification by the Investigator to the Sponsor of an SAE is essential so that legal obligations and ethical responsibilities towards the safety of participants and the safety of a study intervention under clinical investigation are met.
- The Sponsor has a legal responsibility to notify both the local regulatory authority and other regulatory agencies about the safety of a study intervention under clinical investigation. The Sponsor will comply with country-specific regulatory requirements relating to safety reporting to the regulatory authority, Institutional Review Boards (IRB)/Independent Ethics Committees (IEC), and Investigators.
- An Investigator who receives an Investigator safety report describing an SAE or other specific safety information (eg, summary or listing of SAEs) from the Sponsor will review and then file it along with the Investigator's Brochure and will notify the IRB/IEC, if appropriate, according to local requirements.
- Investigator safety reports must be prepared for suspected unexpected serious adverse reactions (SUSAR) according to local regulatory requirements and Sponsor policy and forwarded to Investigators as necessary.

8.5.4.1. Expedited Reporting

The Sponsor/designee will report all relevant information about SUSARs that are fatal or life-threatening as soon as possible to the FDA, applicable competent authorities in all the Member States concerned, and the Central Ethics Committee, and in any case no later than 7 days after knowledge by the Sponsor/designee of such a case. Relevant follow-up information will subsequently be communicated within an additional 8 days.

All other SUSARs will be reported to the FDA, applicable competent authorities concerned, and the Central Ethics Committee concerned as soon as possible but within a maximum of 15 days of first knowledge by the Sponsor/designee.

The Sponsor/designee will also report any additional expedited safety reports required in

accordance with the timelines outlined in country-specific legislation.

The Sponsor/designee will also inform all Investigators as required per local regulation.

The requirements above refer to the requirements relating to the investigational medicinal product.

8.5.5. Pregnancy

- Details of all pregnancies in female participants will be collected after the start of study intervention and until 90 days after the last dose of study intervention.
- If a pregnancy is reported, the Investigator will record pregnancy information on the appropriate form and submit it to the Sponsor within 24 hours of learning of the [female participant or female partner of male participant (after obtaining the necessary signed informed consent from the female partner)] pregnancy.
- While pregnancy itself is not considered to be an AE or SAE, any pregnancy complication or elective termination of a pregnancy for medical reasons will be reported as an AE or SAE.
- Abnormal pregnancy outcomes (eg, spontaneous abortion, fetal death, stillbirth, congenital anomalies, ectopic pregnancy) are considered SAEs and will be reported as such.
- The patient will be followed to determine the outcome of the pregnancy. The Investigator will collect follow-up information on the participant and the neonate and the information will be forwarded to the Sponsor.
- Any post-study pregnancy-related SAE considered reasonably related to the study intervention by the Investigator will be reported to the Sponsor as described in [Section 8.5.4](#). While the Investigator is not obligated to actively seek this information in former study participants, he or she may learn of an SAE through spontaneous reporting.
- Any female participant who becomes pregnant while participating in the study will discontinue study intervention.

8.5.6. Cardiovascular and Death Events

This section is not applicable.

8.5.7. Adverse Events of Special Interest

Adverse events of special interest (AESIs) include infusion-related AEs, acute and chronic GVHD, and CRS. Criteria for acute and chronic GVHD and CRS can be found in Appendix 5 ([Section 10.5](#)) and Appendix 6 ([Section 10.6](#)), respectively.

8.5.7.1. Special Situation Reports

Special situation reports include reports of overdose, misuse, abuse, medication error, and reports of adverse reactions associated with product complaints.

- **Overdose:** Refers to the administration of a quantity of a medicinal product given per

administration or cumulatively (accidentally or intentionally), which is above the maximum recommended dose according to the protocol. Clinical judgement should always be applied. In cases of a discrepancy in the drug accountability, overdose will be established only when it is clear that the patient has taken additional dose(s) or the Investigator has reason to suspect that the patient has taken additional dose(s).

- **Misuse:** Refers to situations where the medicinal product is intentionally and inappropriately used in a way that is not in accordance with the protocol instructions or local prescribing information and may be accompanied by harmful physical and/or psychological effects.
- **Abuse:** Is defined as persistent or sporadic, intentional excessive use of a medicinal product, which is accompanied by harmful physical or psychological effects.
- **Medication error:** Is any unintentional error in the prescribing, dispensing, or administration of a medicinal product by a healthcare professional, patient, or consumer, respectively. The administration or consumption of the unassigned treatment and administration of an expired product are always reportable as medication errors; cases of patients missing doses of investigational product are not considered reportable as medication errors.
- **Product complaint:** Is defined as any written, electronic, or oral communication that alleges deficiencies related to the identity, quality, durability, reliability, safety, effectiveness, or performance of a drug or device after it is released for distribution. A Special Situations Report Form will only be completed if a complaint is associated with an adverse drug reaction.

All special situation events as described above must be reported on the Special Situations Report Form and faxed/mailed to Clinical Research Organization (CRO) Clinical Safety (contact information listed below) within 24 hours of knowledge of the event. All AEs associated with these Special Situations Report Form should be reported as adverse events or SAEs as well as recorded on the AE eCRF and/or the SAE report form. Details of the symptoms and signs, clinical management, and outcome should be provided, when available.

Safety Contact Information: [REDACTED]

[REDACTED]

[REDACTED]

8.6. **Pharmacokinetics**

- Pharmacokinetic parameters are not evaluated in this study.

8.7. **Genetics and/or Pharmacogenomics**

- Genetics are not evaluated in this study.

8.8. Biomarkers

- Biomarkers are not evaluated in this study.

8.9. Immunogenicity Assessments

- Immunogenicity assessments are not evaluated in this study.

8.10. Medical Resource Utilization and Health Economics

- Hospital length of stay and re-admission rates are assessed in this study.

9. STATISTICAL CONSIDERATIONS

9.1. Statistical Hypotheses

The primary statistical hypothesis is that the proportion of patients with clinically significant Adv, BKV, CMV, EBV, HHV-6 and/or JCV infection through Week 14, as determined by an independent, blinded CAC as outlined in Appendix 1 ([Section 10.1.5.2](#)), is less for ALVR105 treated subjects than for subjects treated with Placebo.

9.2. Sample Size Determination

The open label cohort will not be considered in the primary statistical analysis.

9.3. Analysis Populations

For the purposes of analysis, the following analysis populations are defined:

Population	Description
Enrolled	All participants who sign the ICF.
Intent to Treat (ITT)	All randomized patients regardless of whether the patient receives ALVR105 or placebo. All efficacy analyses will be based on the ITT Population. Patients will be analyzed according to their randomized study treatment.
Safety	All patients who receive ALVR105 or placebo. All safety analyses will be based on the Safety Population. Patients will be analyzed according to the treatment actually received.

9.4. Statistical Analyses

The SAP will be finalized prior to database lock and will include a more technical and detailed description of the statistical analyses described in this section. This section is a summary of the planned statistical analyses of the most important endpoints including primary and key secondary endpoints.

9.4.1. General Considerations

Summary statistics will be presented by cohort and treatment group. Unless otherwise stated, continuous variables will be summarized using the number of non-missing observations, arithmetic mean, standard deviation, median, minimum, and maximum values as descriptive statistics. Categorical variables will be summarized using the frequency count and the percentage of patients in each category. All hypothesis tests will be performed at the 0.05 significance level unless otherwise noted.

For time-to-event endpoints, the Kaplan-Meier method will be used to estimate the median time (days) and the corresponding 95% confidence interval for the true median.

9.4.2. Primary Efficacy Endpoint

The primary efficacy endpoint is:

- The primary efficacy endpoint is the proportion of patients with clinically significant AdV, BKV, CMV, EBV, HHV-6 and/or JCV infection (defined as clinically significant infection and/or end-organ disease as determined by an independent, blinded CAC through Week 14).

This endpoint will be summarized by cohort and treatment group using frequency counts and percentages.

9.4.3. Secondary Efficacy Endpoints

The secondary efficacy analysis will be performed on patients in Cohort OL, [REDACTED]

The secondary efficacy endpoints are:

- Time to onset of AdV, BKV, CMV, EBV, HHV-6, and/or JCV viremia at Week 14
- AUC for cumulative viral load for AdV, BKV, CMV, EBV, HHV-6, and JCV over 14 weeks
- Proportion of patients with clinically significant AdV, BKV, CMV, EBV, HHV-6, and/or JCV disease (excludes asymptomatic viremia) through Week 14
- Proportion of patients with clearance of AdV, BKV, CMV, EBV, HHV-6, and/or JCV viremia by Week 8 in HCT patients with detectable viremia prior to the start of treatment
- Proportion of patients with clinically significant AdV, BKV, CMV, EBV, HHV-6, and/or JCV disease and/or end-organ disease as determined by an independent, blinded CAC through Week 26 (the end of the 12-week safety follow-up period)
- Total number of hospital days related to AdV, BKV, CMV, EBV, HHV-6, and/or JCV infection or disease through Week 26
- Proportion of patients with AdV, BKV, CMV, EBV, HHV-6, and/or JCV disease-related mortality through Week 26 as determined by an independent, blinded CAC
- Quality of life assessments, FACT-BMT, EQ-5D-5L, EQ-5D-Y, and EQ-5D-Y Proxy Version 1, through Week 26
- Incidence of overall non-relapse related mortality AdV, BKV, CMV, EBV, HHV 6, and/or JCV disease related mortality as determined by an independent, blinded CAC
- Severity and incidence of acute GVHD
- Severity and incidence of chronic GVHD
- Severity and incidence of CRS
- Severity and incidence of clinically significant cytopenias
- Severity and incidence of renal dysfunction
- Effect on measures of engraftment

Summary tables will be presented by cohort, stratum (Stratum1: Letermovir pretreatment and Stratum 2: No Letermovir pretreatment, and Overall) and [REDACTED]

[REDACTED] For Cohort OL, results will be presented by stratum and overall, as all patients in Cohort OL receive only ALVR105. Combined summary for patients in Cohort OL [REDACTED] will also be provided.

Time to onset of each type of infection (AdV, BKV, CMV, EBV, HHV-6, JCV viremia) and overall will be summarized using Kaplan-Meier method for Cohort OL

Number of patients with onset of AdV, BKV, CMV, EBV, HHV-6, and/or JCV viremia and number of patients censored, and reason of censoring will be presented along with estimate for the median time (days) and its 95% CI.

Time to onset of AdV, BKV, CMV, EBV, HHV-6, and/or JCV viremia will be calculated from the time of randomization until the first date of appearance of any observed viremia. Patients not observed with the onset of AdV, BKV, CMV, EBV, HHV-6, and/or JCV viremia will be censored. Patients who discontinued from the study early before the onset of AdV, BKV, CMV, EBV, HHV-6, and/or JCV viremia will be censored at the last assessment date for this endpoint. Patients who deceased prior to the onset of AdV, BKV, CMV, EBV, HHV-6, and/or JCV viremia will be censored at the last assessment date for this endpoint.

Kaplan-Meier plot for time to onset of AdV, BKV, CMV, EBV, HHV-6, and/or JCV viremia at Week 14 will also be provided for each treatment.

Categorical variables will be summarized using frequency counts and percentages. Continuous variables will be summarized by visit using descriptive statistics.

No adjustment for the multiplicity of secondary and exploratory endpoints will be made for this Phase 2 trial.

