Patients will be tested once a week by the central laboratory during Screening until treatment assignment, using polymerase chain reaction (PCR) assays for each virus. Cohort OL will include patients with and without detectable AdV, BKV, CMV, EBV, HHV-6, and JCV viremia. After Cohort OL, Cohort A will include patients without detectable AdV, BKV, CMV, EBV, HHV-6, and JCV viremia (ie, below the level of quantitation) based on the last viral load assessment available within 7 days prior to randomization, and Cohort B will include patients who are positive with AdV, BKV, CMV, EBV, HHV-6, and/or JCV viremia based on the last viral load available within 7 days prior to randomization, as documented by central laboratory test results. Randomization will occur prior to Day 1. Patients who are positive for >3 viruses will not be eligible to participate.

After HCT, eligible patients in Cohort A and Cohort B will receive either ALVR105 (████████ for patients <40 kg or ██████████ for patients ≥ 40 kg, every 14 days) or placebo every 14 days. Patients in Cohort OL will receive ALVR105 (████████ for patients <40 kg or ██████████ for patients ≥ 40 kg, every 14 days for 14 weeks. Treatment with either ALVR105 or placebo will begin between 15 to 42 (+7) days post-HCT and will continue for 14 weeks. The total duration of patient participation is approximately 28 to 32 weeks, including up to 6 weeks for screening, the 14-week treatment period, and 12 weeks of follow-up.

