^g Clinical laboratory assessments collected as part of standard of care may be used to fulfill these requirements. CBC must include differential and LFTs

must include alkaline phosphatase, bilirubin (direct and indirect); GGT, AST, and ALT. Urinalysis must be performed. Laboratory safety evaluations (hematology, chemistry, and urinalysis) specified in [Section 8.4.4](#) will be performed prior to study drug initiation. These samples will be sent to the appropriate central laboratory(ies) following the procedure(s) described in the study manual(s).

^h For female patients, a urine pregnancy test will be performed at the site prior to study therapy initiation. If the urine pregnancy test result is negative, the patient will be eligible for treatment assignment and the remainder of the Day 1 testing/procedures will be performed. If the urine pregnancy result is positive, the patient must not be assigned to treatment and should reflex to a β -HCG blood test before screen failing. A urine pregnancy test will be performed prior to each treatment for female patients who are of childbearing potential.

ⁱ Viral loads of AdV, BKV, CMV, JCV, and HHV-6 in plasma and of EBV in PCMBs will be measured. Additional post-infusion samples may be collected, as clinically indicated. If patient develops any clinically significant infection of AdV, BKV, CMV, EBV, HHV-6, or JCV at any point during the study periods, infection assessments should be followed prior to initiating standard of care therapy (see [Section 8.3](#)).

^j Patients in Cohort OL will be assigned to ALVR105. Patients in Cohorts A and B will be randomized to either ALVR105 or placebo based upon the last viral load assessed and within 7 days of randomization. Treatment assignment will be about 2 to 3 days before Day 1.

^k Patient peripheral blood mononuclear cells will be assessed for the presence of virus-reactive T cells using enzyme-linked immunospot.

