Study therapy (with ALVR105 or placebo) will begin between 15 and 42 (+7) days (inclusive) post- HCT. Administration may begin as early as day 15 post-HCT as long as, in the Investigator's judgment, the patient has met the engraftment criteria. Study therapy will be given at 2-week intervals through Week 14, and the study evaluation will continue through Week 26 (~6 months), with the primary objective of preventing clinically significant infections and/or disease of AdV, BKV, CMV, EBV, HHV-6, and/or JCV through Week 14 and with a secondary objective of preventing clinically significant infections and/or diseases of AdV, BKV, CMV, EBV, HHV-6, and/or JCV through Week 26 (~6 months). 

On the day of treatment assignment (randomization), eligibility for enrollment into the study should be confirmed (including confirmation that HCT has taken place). 

Once enrolled in the study, patients will have study visits scheduled at weekly intervals through Week 14. Following completion of the primary study period at Week 14, all patients will remain in the study through Week 26 in order to continue collecting information on (1) incidence and time to onset of AdV, BKV, CMV, EBV, HHV-6, and/or JCV viremia and/or disease; (2) all adverse events through the treatment period in all patients, including those who have discontinued study treatment but are continuing in the study. For patients who have discontinued, only drug-related SAEs and SAEs leading to death will be collected until Week 26.; and (3) quality of life (QoL) measures using validated patient reported outcome tools. During the follow-up period, study visits will occur monthly after Week 14 until Week 26. Patients will also receive a follow-up call one year after the Week 26 visit to assess mortality.

For patients who develop any clinically significant infection of AdV, BKV, CMV, EBV, HHV-6, and/or JCV, during the primary study period (up to Week 14) or during the follow-up period (after Week 14 and through Week 26) when the Investigator intends to initiate either treatment for viral infection or disease, infection assessments should be conducted ([Section 8.3](#)). These patients will continue to receive infusions of study drug during the treatment period. 

[figure not shown]
Specific procedures to be performed during the trial, as well as their prescribed times and associated visit windows, are outlined in the SoA ([Section 1.3](#)). Details of each procedure are provided in [Section 8](#).

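### Time to onset of viremia censors deaths as if they were dropouts, so the Kaplan-Meier curve modestly overstates actual onset; time zero and the risk set also need to be stated

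*Protocol*

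**What the plan says.** Time to onset of viremia over 14 weeks is the first secondary endpoint listed in the protocol (1.1, 3 and 9.4.3). Section 9.4.3 sets these rules:

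- **Method.** Onset for each virus and overall "will be summarized using Kaplan-Meier method for Cohort OL"; the text that follows is not legible. The number censored, the reasons for censoring, the median and its 95% CI are reported, with a plot for each treatment.
- **Time zero and event.** Time to onset "will be calculated from the time of randomization until the first date of appearance of any observed viremia".
- **Death.** "Patients who deceased prior to the onset of AdV, BKV, CMV, EBV, HHV-6, and/or JCV viremia will be censored at the last assessment date". Early discontinuation gets the same treatment.

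On allocation, the footnotes to the Schedules of Activities (1.3) say: "Patients in Cohort OL will be assigned to ALVR105. Patients in Cohorts A and B will be randomized to either ALVR105 or placebo". They add: "Treatment assignment will be about 2 to 3 days before Day 1". Section 4.1 uses the two terms as one: "On the day of treatment assignment (randomization), eligibility for enrollment into the study should be confirmed".

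On viremia at entry, the Synopsis says "Cohort OL will include patients with and without detectable AdV, BKV, CMV, EBV, HHV-6, and JCV viremia" and "Cohort B will include patients who are positive with AdV, BKV, CMV, EBV, HHV-6, and/or JCV viremia". Patients positive for more than three viruses are ineligible.

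The SAP covers Cohort OL only and states that its analysis follows Amendment 4. Its endpoints (2.3.1 to 2.3.3) do not include time to onset of viremia, and it has no Kaplan-Meier analysis. It counts study days from first dose (3.1.1).

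**The concern.** Censoring is suitable for a patient who leaves observation but could still have the event. Death before viremia removes that possibility. Kaplan-Meier with deaths censored in effect spreads the dead patients' remaining risk over the survivors, so the curve rises above the proportion who actually become viremic and the median comes early. Death cannot be set aside in this population: the protocol names viral infection as a leading cause of transplant-related mortality and has mortality among its secondary endpoints. In the randomized cohorts, unequal deaths between arms would also distort the comparison that the first secondary objective calls for.

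The two lesser points concern what is being timed. An origin at randomization does not literally apply to a cohort that is not randomized. An event defined as first observed viremia needs a rule for patients who are viremic before the clock starts.

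**Working it through.** The plan states no median, event rate, death rate or share viremic at entry for this endpoint, so there is no figure to reproduce. What follows is illustration.

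**Inputs.** From the documents: 14 weeks = 98 days; Cohort OL of 25 to 35 patients (30 used); assignment 2 to 3 days before Day 1; at most three viremias at entry. Assumed: constant hazards, 14-week viremia V of 30% to 90%, 14-week mortality D of 5% to 20%, and share b viremic at entry of 10% to 50%. The 90% end of V echoes the reactivation rate that Protocol 2.2 cites.

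**1. Death.** With λv = −ln(1−V) and λd = −ln(1−D) per 98 days:

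- One minus Kaplan-Meier, deaths censored = V.
- Cumulative incidence with death competing = λv/(λv+λd) × [1 − (1−V)(1−D)].

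For V = 0.70 and D = 0.10: λv = 1.2040, λd = 0.1054, sum 1.3093. Then (1.2040/1.3093) × (1 − 0.30 × 0.90) = 0.9195 × 0.73 = 0.671, against 0.700.

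Cumulative incidence at day 98, with the Kaplan-Meier excess in points:

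| V | D = 5% | D = 10% | D = 20% |
|---|---|---|---|
| 30% | 0.293 (0.7) | 0.286 (1.4) | 0.271 (2.9) |
| 50% | 0.489 (1.1) | 0.477 (2.3) | 0.454 (4.6) |
| 70% | 0.686 (1.4) | 0.671 (2.9) | 0.641 (5.9) |
| 90% | 0.885 (1.5) | 0.870 (3.0) | 0.839 (6.1) |

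The Kaplan-Meier median is 98 × ln 2/λv. At V = 70% it is 56.4 days, while cumulative incidence reaches 50% at 58.7 days (D = 10%) or 61.7 days (D = 20%). At V = 50% and D = 10%, Kaplan-Meier gives a median at day 98, but cumulative incidence is only 0.477 by then and has no median in the window.

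Simulation with 30 patients, weekly sampling and deaths censored at the last visit (4,000 runs per setting) agrees:

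| V, D | Mean 1−KM | Proportion with onset | SD of 1−KM |
|---|---|---|---|
| 50%, 10% | 0.502 | 0.477 | 0.096 |
| 70%, 10% | 0.700 | 0.669 | 0.086 |
| 70%, 20% | 0.700 | 0.636 | 0.089 |
| 90%, 10% | 0.900 | 0.867 | 0.057 |

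**2. Time zero.** Starting at assignment instead of first dose moves the median by 2 to 3 days. That is 3.5% to 5.3% of a 56.4-day median, or 6.8% to 10.2% of the 29.5-day median at V = 90%.

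**3. Viremic at entry.** If a share b were counted as events at time 0, the overall curve would be b + (1−b) × [1 − exp(−λv t/98)], with median 98 × ln[2(1−b)]/λv for b below 50%. At V = 70% among the rest, the median falls from 56.4 days to 47.8, 38.3, 27.4 and 14.8 days for b = 10%, 20%, 30% and 40%, and to 0 at b = 50%. For b = 30%: 98 × ln(1.4)/1.2040 = 27.4. This is the largest of the three effects, but it depends on a counting convention that the protocol does not state.

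**The case against.** **Death as censoring can be a deliberate choice of target.** Kaplan-Meier then describes onset in the absence of death, and the reported reasons for censoring would disclose the deaths. The visible summary is a median and a plot, not a 14-week percentage, and no test is visible. This stands in part: the estimate is not meaningless. But the protocol does not say that a risk without death is the target. That reading also needs patients who die to have had the same viremia risk as those who survive. Listing reasons does not change the curve.

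**The analysis may never be run in Cohort OL.** The SAP follows Amendment 4 and summarises detectable viremia by visit and viral-load AUC per day instead. It describes a Phase 2/3 trial with a count endpoint, whereas the supplied protocol is Phase 2 with a proportion. The endpoint may have been dropped between versions; that is an inference. This limits the practical effect. Still, the protocol names Cohort OL for this analysis. The SAP explains why hospitalization and engraftment data are not analysed, but says nothing about this endpoint.

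**A reader might infer that the endpoint is undefined in Cohort OL.** The documents do not support that. Section 4.1 equates treatment assignment with randomization, so the assignment date is a natural reading and the cost is 2 to 3 days.

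**A reader might also infer that patients already viremic are included, making the endpoint degenerate in Cohort B.** That rests on silence in a partly redacted section. The word onset points towards excluding them, and patients viremic before treatment have a separate clearance endpoint. Curves are also planned for each virus: with at most three viremias at entry, every patient is free of at least 6 − 3 = 3 viruses and can have a true onset. Only an overall curve that counts baseline viremia as an event would collapse.

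**Conclusion.** The point holds for the death rule, which is stated outright. Deaths are censored like dropouts, so the curve overstates actual onset and its median comes early. The direction is certain whenever patients die before onset. The size is not, because both rates are assumed: 0.7 to 6.1 points at 14 weeks, modest against a standard error of about 6 to 10 points at n = 30. It would be too strong to conclude that the curve and median are simply wrong, since they answer a different, hypothetical question.

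The origin is an ambiguity of 2 to 3 days. The risk set is a rule that is not visible, and it would matter most if baseline viremia were counted at time 0. The SAP's omission of the endpoint reduces the consequence for Cohort OL but does not correct the protocol's rule.

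**What to change.** In Protocol 9.4.3, and in any SAP that carries this endpoint:

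1. Report cumulative incidence of onset with death before viremia as a competing event (Aalen-Johansen). Early discontinuation stays as censoring.
2. Measure from first dose in Cohort OL, consistent with SAP 3.1.1, and from randomization in Cohorts A and B.
3. For each virus, include only patients below LLOQ for that virus at baseline. For the overall curve, choose in advance between patients below LLOQ for all six viruses and time to the first new virus.
4. If the endpoint will not be analysed in Cohort OL, record its removal and the reason in the SAP.

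The cost is wording and slightly more analysis work with standard software, with no new data to collect. The risk set for each virus becomes smaller, so those estimates will be less precise.
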